### **Considerations for making a change**

The prevailing consideration for making a change is ensuring the safety of study participants. Additional important considerations for making a change are compliance with Good Clinical Practice, enabling participants to continue safely in the study and maintaining the integrity of the study.

### **Informed consent**

Additional consent from the participant will be obtained, if required, for:

- participation in remote visits, as defined in Section "Remote Visits,"
- a change in the method of study intervention administration,
- dispensation of additional study intervention during an extended treatment period,
- alternate delivery of study intervention and ancillary supplies, and
- provision of their personal or medical information required prior to implementation of these activities.

### **Changes in study conduct during exceptional circumstances**

Changes in study conduct not described in this appendix, or not consistent with applicable local regulations, are not allowed.

The following changes in study conduct will not be considered protocol deviations.

#### ***Remote visits***

##### ***Types of remote visits***

In source documents and the electronic Case Report Form (eCRF), the study site should capture the visit location and the method (e.g., telemedicine, mobile healthcare, etc.), with a specific explanation that includes the term ‘COVID-19 related’ (when applicable) for any data missing because of missed in-person site visits.

**Telemedicine:** Telephone or technology-assisted virtual visits, or both, are acceptable to complete appropriate assessments. Assessments to be completed in this manner include, but are not limited to, concomitant medications, review of systems, Eastern Cooperative Oncology Group (ECOG) performance status (PS), dosing information, patient reported outcome measures, and information regarding local healthcare utilization/hospitalization.

**Mobile healthcare:** Healthcare visits may be performed by a mobile healthcare provider at locations other than the study site when patients cannot travel to the site due to an exceptional circumstance if written approval is provided by the Sponsor. Procedures performed at such visits include, but are not limited to, review of systems, physical examinations, and laboratory studies (e.g., hematology, chemistry, etc.).

**Other alternative locations:** Other procedures that may be done at an alternative location in exceptional circumstances include, but are not limited to, review of systems, physical examination, electrocardiogram (ECG) tracings, laboratory studies (e.g., hematology, chemistry), and radiologic imaging.

Regardless of the type of remote visits implemented, the protocol requirements regarding the reporting of adverse events (AEs), serious adverse events (SAEs), and product complaints remain unchanged. Furthermore, every effort should be made to enable patients to return to on-site visits as soon as reasonably possible, while ensuring the safety of both the patients and the site staff.

#### **Local laboratory testing option**

Local laboratory testing may be conducted in lieu of central laboratory testing. The local laboratory must be qualified in accordance with applicable local regulations.

### **Study intervention and ancillary supplies (including participant diaries)**

When a participant is unable to go to the site to receive study supplies (including study drug) during normal on-site visits, the site should work with the sponsor to determine appropriate actions. These actions may include:

- asking the participant to go to the site and receive study supplies from site staff without completion of a full study visit,
- asking the participant's designee to go to the site and receive study supplies on a participant's behalf, and
- arranging delivery of study supplies.

These requirements must be met before action is taken:

- Alternate delivery of study intervention should be performed in a manner that does not compromise treatment blinding and ensures product integrity. The existing protocol requirements for product accountability remain unchanged, including verification of participant's receipt of study supplies.
- When delivering supplies to a location other than the study site (for example, participant's home), the investigator, sponsor, or both should ensure oversight of the shipping process to ensure accountability and product quality (that is, storage conditions maintained and intact packaging upon receipt).
- Instructions may be provided to the participant or designee on the final disposition of any unused or completed study supplies.

### **Documentation**

#### *Changes to study conduct will be documented*

Sites will identify and document the details of how participants, visits types, and conducted activities were affected by exceptional circumstances. Dispensing/shipment records of study intervention and relevant communications, including delegation, should be filed with site study records.

#### *Source documents at alternate locations*

Source documents generated at a location other than the study site should be part of the investigator's source documentation and should be transferred to the site in a secure and timely manner.

## Appendix M Protocol Amendment History

The Protocol Amendment Summary of Changes Table for the current amendment is located directly before the Table of Contents (TOC).

### Amendment [11.0]

This amendment is considered to be substantial.

The amendment is considered to be substantial because it is likely to have a significant impact on the

- safety or the rights of the study participants, and
- reliability and robustness of the data generated in the clinical study.

### Overall Rationale for the Amendment:

The purpose of this amendment is provided in the table below.

Section # and Name	Description of Change	Brief Rationale
Synopsis	Updated to match changes in the main protocol	Alignment with main protocol updates
Section 1.7 Clinical Experience; Section 1.7.1. Known and Anticipated Risks	Updated data and simplified list of AEs of special interest	Update
Section 3.1 Study Design	Sentence added in regard to In Vitro Diagnostic Regulation	Update
Section 3.2.1. Length of Study	Added language regarding end of study and continued access	Update to study design

Section # and Name	Description of Change	Brief Rationale
Section 3.2.1 Length of Study and Section 3.4 Phase 1 and Maximum Tolerated Dose Determination; Section 3.7 Definition of RET Alterations; Table 3-3 Definition of RET Alterations; Section 4.1. Inclusion Criteria for Phase 1	Added statement regarding RET alteration result should be generated as per local guidelines including but not limited to IVDR compliance as applicable	To comply with the IVDR and ensure that RET testing meets EU clinical laboratory requirements
Section 3.2.2. End of Study	Added language regarding continued access follow-up	Update to study design
Section 3.6 Phase 2; Section 4.2 Inclusion Criteria for Phase 2; Section 4.3. Exclusion Criteria for Phase 2	
 
Removed Cohort 7 wording
 
Deleted exclusion criterion 16
 
	
 
Align with leadership decision to end enrolment to most populations and remove cohort 7
 

Section 3.6. Phase 2; Figure 3-1 Study Schema	
 
Updated total number of patients and cohort patient distribution
 
Excluded Germany from Cohort 2 and 4
 
Deleted language regarding Cohort 8 wording
 
Updated language regarding cycle length
 
Updated study schema
 
	
 
Align with leadership decision to end enrolment to most populations and remove cohort 7
 
Clarification
 
Correction
 
Update
 

Section 3.8. Number of Patients	
 
Updated total number of patients from 950 to 875
 
	Align with leadership decision to end enrolment to most populations and remove cohort 7

Section # and Name	Description of Change	Brief Rationale
Section 4.1. Inclusion Criteria for Phase 1	
 
Updated inclusion criterion 13: birth control duration changed from 3 months to 1 month
 
Moved inclusion criterion 14 to Appendix K: Country-specific Requirement
 
	
 
To align with label
 
For harmonization of the protocol and to avoid country and region-specific protocol versions in the EU
 

Section 6.1. Investigational Product	
 
Simplified language regarding selpercatinib provision
 
	Clarification
Section 6.3.2. Allowed Concomitant Medications	
 
Clarified language regarding dose restriction for administration routes for systemic glucocorticoids
 
	
Section 6.4. Removal of Patients from Therapy or Assessment	
 
Remove requirement for additional consultation/approval of post progression continuation (2nd or further PD)
 
Moved note for Germany into Appendix K: Country-specific Requirements
 
	
 
Per new requirements
 
For harmonization of the protocol and to avoid country and region-specific protocol versions in the EU
 

Table 7-1 Schedule of Assessments; Section 7.3. Cycles 2 and Higher	
 
12-lead ECG: added language in Cycle 7 column regarding ECG assessments until cycle 26 and beyond as clinically indicated; updated footnote "j".
 
	Clarification

Section # and Name	Description of Change	Brief Rationale
Table 7-1 Schedule of Assessments; Section 7.3 Cycles 2 and Higher	
 
Clarified that Urinalysis will be conducted "as clinically indicated" beyond C1D15; updated footnote "q"
 
	Clarification
Table 7-1 Schedule of Assessments; Section 7.3. Cycles 2 and Higher; Section 7.8.5.3. Blood Biomarkers	
 
Whole blood for cfDNA analysis: updated number of collections; updated footnote "u"
 
	To reduce the burden on patients.
Table 7-1 Schedule of Assessments; Section 7.3. Cycles 2 and Higher	
 
Updated language in Cycle 7-higher column
 
	To align with local standard-of-care
Section 7.8.5.3. Blood Biomarkers	
 
Added language on use of samples
 
	Addition
Section 7.8.5.4 Biomarker Samples	
 
Added section
 
	Clarification on use of biomarker samples
Section 7.9. Continued Access	
 
Added section
 
	Update to study design
Section 8.2.1. Safety Analysis Set	
 
Deleted statement regarding efficacy analysis
 
	Clarification
Section 8.3. Determination of Sample Size	
 
Deleted language regarding exploring efficacy in patients with oncogenic drivers
 
	Correction

Section # and Name	Description of Change	Brief Rationale
Section 8.5.1. Demographics and Baseline Characteristics; Section 8.5.2. Safety Analyses	
 
Clarified that patients will be tabulated, and safety analyses will be presented by tumor indication
 
	Clarification
Section 8.5.3. Efficacy Analyses	
 
Updated language; added reference to SAP
 
	Update
Section 8.5.4. Pharmacokinetic Analyses	
 
Updated language to match with Synopsis
 
	Correction
Section 9.1. Safety Review Committee	
 
Clarified that Phase 2 safety committee will convene every 6 months for the first 5 years, and then annually
 
Removed language regarding additional SRC meetings after every fifth patient between ages 12 and 17
 
	Aligned with Safety Steering Committee
Appendix K: Country-specific Requirements	
 
Added new section to capture protocol changes applicable for participants in study sites in Germany
 
	Addition
Appendix L: Provisions for Changes in Study Conduct During Exceptional Circumstances	
 
Added new section to capture provisions for changes in study conduct during exceptional circumstances
 
	Addition

Section # and Name	Description of Change	Brief Rationale
Appendix M: Protocol Amendment History	

Added new section to capture amendment history

	Addition
Throughout	Minor editorial and document formatting revisions.	These are minor changes; therefore, they have not been summarized

4.4. Exploratory Endpoint Analysis	21
4.4.1. Disease Control Rate	21
4.4.2. Intra-patient Analysis	21
4.5. Other Safety Analyses	21
4.5.1. Vital Signs	21
4.5.2. Body Weight	22
4.5.3. Performance Status	22
4.5.4. Adverse Events of Special Interest	22
4.5.5. Electrocardiograms	23

4.5.6.	Extent of Exposure.....	24
4.6.	Other Analyses	24
4.6.1.	Subgroup analyses.....	24
4.7.	Changes to Protocol-Planned Analyses.....	25
5.	Supporting Documentation.....	26
5.1.	Appendix 1: Demographic and Baseline Characteristics	26
5.1.1.	Demography.....	26
5.1.2.	Cancer History	26
5.1.3.	Prior Cancer Treatment.....	27
5.1.4.	RET Alteration Status	27
5.1.5.	Noncancer Medical History	27
5.2.	Appendix 2: Protocol Deviation.....	27
6.	References	28

Abbreviations and Definitions

Term	Definition
ADI	actual dose intensity
AE	adverse events
ALT	alkaline phosphatase, albumin, alanine transaminase
AST	aspartate aminotransferase
BOR	best overall response
CBR	clinical benefit rate
CEA	carcinoembryonic antigen
CI	confidence interval
CNS	central nervous system
CR	complete response
CSR	clinical study report
CTCAE	Common Terminology Criteria for Adverse Events
DCR	disease control rate
DOR	duration of response
ECG	electrocardiogram
ECOG	Eastern Cooperative Oncology Group
IRC	independent review committee
Lilly	Eli Lilly and Company
MedDRA	Medical Dictionary for Regulatory Activities
MTC	medullary thyroid cancer
NE	not evaluable
NSCLC	non-small cell lung cancer
ORR	overall response rate
OS	overall survival
PD	progressive disease
PDI	planned dose intensity
PFS	progression-free survival
PR	partial response
QTcF	Fridericia's Correction Formula
RDI	relative dose intensity

Term	Definition
RECIST	Response Evaluation Criteria in Solid Tumours
RET	rearranged during transfection
SAE	serious adverse events
SAP	statistical analysis plan
SD	stable disease
TOT	time on treatment
TTBR	time to best response
TTR	time to response
ULN	upper limit of normal

Version history

Table JZJA.1.1. SAP Version History Summary

SAP Version	Approval Date	Change	Rationale
1	07 August 2019	Not Applicable	Original version
2	07 May 20021	Define analysis and analysis set for the Japan regulatory submission	Before the data cutoff for the Japan regulatory submission
3	See date on Page 1	Define analysis and analysis set for the final clinical study report	To define the analysis set for the final clinical study report

1. Introduction

The purpose of this SAP is to define the analysis set for the final clinical study report of J2G-OX-JZJA (JZJA) and document the statistical methods to be used to demonstrate the effectiveness and the safety of selpercatinib in patients with *RET* advanced solid tumors, including *RET* fusion-positive NSCLC, thyroid, medullary thyroid cancer, and other tumors with *RET* activation.

1.1. Objectives and Endpoints

Objectives	Endpoints
Primary	

 Assess the antitumor activity of selpercatinib in patients with Advanced Solid Tumors, including RET fusion-positive solid tumors, medullary thyroid cancer, and other tumors with RET activation 	
 ORR based on IRC assessment using RECIST 1.1
Secondary	

 Assess the antitumor activity of selpercatinib in patients with Advanced Solid Tumors, including RET fusion-positive solid tumors, medullary thyroid cancer, and other tumors with RET activation 	
 ORR based on investigator assessment using RECIST 1.1 CNS ORR (by IRC; patients with RET fusion NSCLC and brain metastases) CNS DOR (by IRC; patients with RET fusion NSCLC and brain metastases) Biochemical response TTR (by IRC and investigator) TTBR (by IRC and investigator) DOR (by IRC and investigator) CBR (by IRC and investigator) PFS (by IRC and investigator) OS

 Determine the safety profile and tolerability of selpercatinib in patients with Advanced Solid Tumors, including RET fusion-positive solid tumors, medullary thyroid cancer, and other tumors with RET activation 	
 Safety per CTCAE (including but not limited to): frequency and severity of TEAEs, SAEs, deaths, and clinical laboratory abnormalities Changes in haematology and blood chemistry values Assessments of physical examinations Vital signs, and ECGs

 To characterize the PK properties of selpercatinib 	
 Plasma concentrations of selpercatinib and PK parameters, including, but not limited to, AUC_{0-24}, C_{max}, and T_{max}

Abbreviations: AUC_{0-24} = area under the plasma concentration-time curve from 0 to 24 hours; C_{max} = maximum observed drug concentration; CTCAE = Common Terminology Criteria for Adverse Events; CBR = clinical benefit rate; CNS = central nervous system; DOR = duration of response; ECGs = electrocardiograms; IRC = independent review committee; NSCLC = non-small cell lung cancer; ORR = overall response rate; OS = overall survival; PFS = progression-free survival; PK = pharmacokinetic; RECIST = Response Evaluation Criteria in Solid Tumors; *RET* = Rearranged during Transfection; SAE = severe adverse event; TEAE = treatment-emergent adverse event; T_{max} = time to maximum plasma; TTBR = time to best response; TTR = time to response.

1.2. Study Design

This is an open-label, multicenter, Phase 1/2 study in patients with advanced solid tumors, including *RET* fusion-positive solid tumors (for example, NSCLC and thyroid), *RET*-mutant MTC, and other tumors with *RET* activation (for example, mutations in other tumor types or

other evidence of *RET* activation). This study includes 2 parts: Phase 1 (dose escalation and dose expansion) and Phase 2.

A detailed description of the study design is contained in the protocol.

2. Analysis Sets

For the purposes of analysis, the following analysis sets are defined.

2.1. Safety Analysis Set

[Table JZJA.2.1](#) provides an overview of the safety analysis set.

Table JZJA.2.1. Description of Safety Analysis Sets

Safety Analysis Set	Analysis Set Description
Overall Safety Analysis Set	All patients who received at least 1 or more doses of selpercatinib regardless of diagnosis or line of therapy
RET fusion-positive NSCLC safety analysis set	All patients with RET fusion-positive NSCLC who received at least 1 dose of selpercatinib. This is a subset of the Overall Safety Population.
RET mutant MTC safety analysis set	All patients with RET mutant MTC who received at least 1 dose of selpercatinib. This is a subset of the Overall Safety Population.
RET fusion-positive thyroid safety analysis set	All patients with RET fusion-positive thyroid who received at least 1 dose of selpercatinib. This is a subset of the Overall Safety Population.
RET mutant non-MTC safety analysis set ^a	All patients with RET mutant non-MTC who received at least 1 dose of selpercatinib. This is a subset of the Overall Safety Population.
Prior RET inhibitor safety analysis set ^a	All patients who have received prior treatment with a selective RET inhibitor. This is a subset of the Overall Safety Population. This group includes patients with RET fusion-positive NSCLC, RET fusion-positive Thyroid and RET mutant MTC.

Abbreviations: MTC = medullary thyroid cancer; NSCLC = non-small cell lung cancer; *RET* = Rearranged during Transfection.

^a Selected safety analyses will be performed.

As of the data cutoff, enrollment is still ongoing for *RET* fusion-positive cancer other than NSCLC and thyroid cancer and the safety analysis and efficacy analysis on the population will be included in the respective CSR.

2.2. Efficacy Analysis Set

Patients who received at least 1 dose of selpercatinib and achieved at least 6 months of potential follow-up time from the first dose of selpercatinib (or disease progression or death, whichever occurred first), as of a data cutoff, will be considered eligible for efficacy analyses. The efficacy analysis sets are defined by tumor diagnosis and line of therapy and described in [Table JZJA.2.2](#).

Table JZJA.2.2. Description of efficacy Analysis Sets

Tumor Diagnosis/Line of Therapy	Analysis Set	Analysis Set Description
RET fusion-positive NSCLC	Patients Previously Treated with Platinum-Based Chemotherapy	Efficacy eligible patients with RET fusion-positive NSCLC previously treated with platinum-based chemotherapy.
	Treatment-Naïve Patients	Efficacy eligible treatment-naïve patients with RET fusion-positive NSCLC.

Tumor Diagnosis/Line of Therapy	Analysis Set	Analysis Set Description
	Patients Previously Treated with Other Systemic Therapy	Efficacy eligible patients with RET fusion-positive NSCLC previously treated with systemic therapies other than platinum-based chemotherapy.
	Patients with Non-measurable disease	Efficacy eligible patients with RET fusion-positive NSCLC previously treated and treatment-naïve patients without measurable disease by RECIST v1.1.
	CNS Response Analysis Set	Efficacy eligible patients with RET fusion-positive NSCLC who had investigator-identified CNS metastases at baseline (reported as target or nontarget lesion per RECIST v1.1).
RET mutant MTC	Patients Not Previously Treated with Cabozantinib and/or Vandetanib	Efficacy eligible patients with RET -mutant MTC that have had no prior systemic therapy or have been treated with a prior systemic therapy besides cabozantinib and vandetanib.
	Patients Previously Treated with Cabozantinib and/or Vandetanib	Efficacy eligible patients with RET -mutant MTC treated with cabozantinib and/or vandetanib.
	Patients with Non-Measurable Disease	Efficacy eligible patients with RET -mutant MTC previously treated and treatment naïve patients without measurable disease by RECIST v1.1
	Patients Naïve to Any Systemic Therapy	This analysis set is a subset of the ‘Patients Not Previously Treated with Cabozantinib and/or Vandetanib’ analysis set
	Patients Naïve to Cabozantinib and Vandetanib But Previously Treated with Other Systemic Therapy	This analysis set is a subset of the ‘Patients Not Previously Treated with Cabozantinib and/or Vandetanib’ analysis set
RET fusion-positive thyroid	Patients Not Previously Treated with systemic therapy other than RAI	Efficacy eligible patients with RET fusion-positive TC that have had no prior systemic therapy (lenvatinib, sorafenib) other than RAI
	Patients Previously Treated with systemic therapy other than RAI	Efficacy eligible patients with RET fusion-positive TC previously treated with systemic therapy (lenvatinib, sorafenib) other than RAI
RET mutant non-MTC ^a	Patients with RET mutant non-MTC	Efficacy eligible patients with RET mutant non-MTC
Prior RET inhibitor ^{a,b}	Patients who have received prior treatment with a selective RET inhibitor	Efficacy eligible patients with a prior selective RET inhibitor

Abbreviations: CNS = central nervous system; MTC = medullary thyroid cancer; NSCLC = non-small cell lung cancer; RAI = radioactive iodine; RECIST = Response Evaluation Criteria in Solid Tumours; *RET* = Rearranged during Transfection; TC = thyroid cancer.

^a Selected efficacy analysis will be performed.

^b This group includes patients with *RET* fusion NSCLC, *RET* fusion thyroid, and *RET* mutant MTC and is excluded from the other efficacy analysis sets.

3. Data Cutoff

A data cutoff date will be announced when prespecified requirement in population of patients with *RET* fusion-positive thyroid is met.

Among at least 50 *RET* fusion-positive thyroid cancer who have received radioactive iodine (if appropriate for their tumor histology), all responding patients have been followed for 12 months following onset of response by investigator assessment or until disease progression, whichever comes first.

4. Statistical Analyses

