**Secondary Objectives (Phase 2):**

- To assess, for each expansion cohort, the anti-tumor activity of selpercatinib by determining:
  - ORR based on RECIST 1.1 or RANO, as appropriate to tumor type, as assessed by Investigator;
  - Best change in tumor size from baseline as assessed by IRC and Investigator;
  - Duration of response (DOR) as assessed by IRC and Investigator;
  - Central nervous system (CNS) ORR based on RECIST 1.1 or RANO, as appropriate to tumor type, as assessed by IRC (for patients with brain metastases);
  - CNS DOR as assessed by IRC (for patients with brain metastases);
  - Time to any and best response based on RECIST 1.1 or RANO, as appropriate to tumor type, as assessed by IRC and Investigator;
  - Clinical Benefit Rate (CBR) based on the proportion of patients with best overall response of complete response (CR), partial response (PR), or stable disease (SD) lasting 16 or more weeks following initiation of selpercatinib as assessed by IRC and Investigator;
  - Progression-free survival (PFS) as assessed by IRC and Investigator;
  - Overall survival (OS) following initiation of selpercatinib.
- To determine the safety profile and tolerability of selpercatinib.
- To characterize the PK properties of selpercatinib.

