- v. Baseline disease assessment with radiographic tumor measurements using CT or MRI of chest, abdomen, and pelvis or any other areas with suspected disease involvement within 28 days of C1D1. During Phase 2, brain imaging is required at baseline for all RET fusion-positive patients, patients with a history of CNS metastases, or other patients if clinically indicated and subsequent serial scans if brain metastases are present at baseline (MRI preferred, CT with contrast is acceptable if MRI contraindicated). For each modality, IV and oral contrast should be utilized (chest CT does not require IV contrast) unless there is a clear contraindication (e.g., decreased renal function or allergy that cannot be addressed with standard prophylactic treatments). In the absence of known or suspected disease involvement, head and neck CT/MRI scans are not required for malignancies other than those originating in the head and neck region. Other areas of scanning may also differ depending on disease type. Post-baseline scans should be performed every 8 weeks ( $\pm 7$  days) for one year and every 12 weeks ( $\pm 7$  days) thereafter, including imaging of the chest, abdomen, and pelvis, using the same modality(ies) as used for baseline imaging assessment until PD, withdrawal of consent, or initiation of a new anticancer therapy(ies). Additionally, any studies performed at baseline that are positive for sites of disease should be repeated at all post-baseline assessments. Additional studies can also be performed as clinically indicated. In addition, Investigators may conduct an initial tumor evaluation on C2D1 ( $\pm 7$  days) and a confirmatory tumor evaluation a minimum of 4 weeks (i.e., 28 days) after the first tumor evaluation that shows a CR or PR by RECIST 1.1 (or RANO, as appropriate to tumor type), if consistent with local regulatory authority requirements. In addition, an initial post baseline assessment on C2D1 ( $\pm 7$  days) is encouraged if consistent with regulatory guidelines. If a scan is performed on C2D1, the next scan should continue according to the schedule above (beginning at C3D1). All scans will be collected and stored at a central facility to permit central reviewer assessment if desired. Please see the Site Imaging Manual for guidelines on how the various imaging studies should be performed.
- w. If not performed within the last 8 weeks.

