4.3.1. Definition of Endpoint

BOR for each patient (CR, PR, SD, PD, or inevaluable) occurring between the first dose of selpercatinib and the date of documented disease progression or the date of subsequent anticancer therapy or cancer-related surgery will be determined based on the RECIST 1.1. All objective responses will be confirmed by a second scan at least 28 days after the initial response.

BOR will be summarized descriptively to show the number and percentage of patients in each response category. Waterfall plots may be used to depict graphically the maximum decrease from baseline in the sum of the diameters of target lesions.

The estimate of ORR will be calculated based on the maximum likelihood estimator (that is, crude proportion of patients with BOR of CR or PR). The estimate of the ORR will be accompanied by 2-sided 95% exact binomial CI.

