4.3.4. CNS ORR and CNS DOR

The CNS ORR and CNS DOR will be assessed by IRC only according to the IRC charter and will be analyzed using the same method described above for the analyses of ORR and DOR.

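### CNS ORR is read by the IRC in a set chosen by the investigator, so patients with no IRC-identified baseline CNS lesion appear to dilute it; an IRC-confirmed subset should be reported alongside

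*SAP*

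**What the plan says.** Two readers are involved.

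- **Denominator.** SAP 2.2, Table JZJA.2.2, forms the CNS Response Analysis Set from efficacy-eligible RET fusion-positive NSCLC patients with "investigator-identified CNS metastases at baseline (reported as target or nontarget lesion per RECIST v1.1". IRC confirmation is not required, and the table has no second CNS set.
- **Numerator.** SAP 4.3.4: "The CNS ORR and CNS DOR will be assessed by IRC only according to the IRC charter". The results "will be analyzed using the same method described above for the analyses of ORR and DOR".
- **Estimator.** SAP 4.3.1 defines ORR as the "crude proportion of patients with BOR of CR or PR". The categories are listed as "BOR for each patient (CR, PR, SD, PD, or inevaluable", and nothing limits the denominator to evaluable patients. On precision: "The estimate of the ORR will be accompanied by 2-sided 95% exact binomial CI".
- **Protocol population.** Among the Phase 2 secondary objectives, CNS ORR is to be determined "as assessed by IRC (for patients with brain metastases". The protocol does not say whose reading establishes the metastases.
- **Baseline imaging.** In Protocol Table 7-1, footnote v, for Phase 2, "brain imaging is required at baseline for all RET fusion-positive patients".

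**The concern.** The investigator decides who is counted and the IRC decides who has responded. The two need not agree at baseline. Exclusion criterion 7 (Protocol 4.3) admits patients whose CNS disease is stable after earlier surgery or radiation, and a non-target lesion is enough to enter the CNS set. Small or already treated lesions of that kind are ones on which two readers could differ.

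If the IRC sees no baseline CNS lesion, there is nothing in which it can record a CNS response. CNS ORR would then fall with reader disagreement as well as with lack of drug activity, and a reader of the study report could not separate the two. The 2×2 agreement table in SAP 4.3.2 is placed under ORR by investigator. It is not specified for identification of CNS lesions at baseline, so the report need not show how many patients are affected.

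**Working it through.** The documents give no CNS set size, no expected CNS ORR and no baseline agreement rate, so there is no planned figure to reproduce. The check has two parts.

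**1. Does the consequence follow from the text?**

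- A patient with an investigator-reported brain lesion is in the set (SAP 2.2). No later SAP section removes that patient if the IRC disagrees.
- Response is taken from the IRC alone (SAP 4.3.4).
- Protocol Table 11-10 reaches an overall CR or PR only through target or non-target lesions. A patient with neither on the IRC read has no row leading to CR or PR.
- The estimator divides responders by all patients in the set, and inevaluable is a best-response category that is not a response (SAP 4.3.1).

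Taken together, the patient counts in the denominator and cannot count in the numerator. This is an inference from four places; no single sentence states it.

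**2. How large could it be?**

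Let d be the share of the set with no IRC-identified baseline CNS lesion, and R the CNS ORR among the remainder. Then

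CNS ORR in the SAP set = (1 − d) × R.

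With R = 80% (assumed): 0.90 × 80% = 72%; 0.80 × 80% = 64%; 0.70 × 80% = 56%.

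The loss in percentage points is d × R. For assumed R between 50% and 85%:

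| d | Loss at R = 50% | Loss at R = 85% |
|---|---|---|
| 10% | 5.0 | 8.5 |
| 20% | 10.0 | 17.0 |
| 30% | 15.0 | 25.5 |

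With exact (Clopper-Pearson) 95% intervals, for an assumed 80 investigator-identified patients and R of about 70%, rounded to whole patients:

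| d | SAP set | IRC-confirmed patients only |
|---|---|---|
| 10% | 50/80 = 62.5% (51.0–73.1) | 50/72 = 69.4% (57.5–79.8) |
| 20% | 45/80 = 56.2% (44.7–67.3) | 45/64 = 70.3% (57.6–81.1) |
| 30% | 39/80 = 48.8% (37.4–60.2) | 39/56 = 69.6% (55.9–81.2) |

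At d = 20% the interval width goes from 67.3 − 44.7 = 22.6 points to 81.1 − 57.6 = 23.5 points. In this example the loss of precision is small beside the shift in the estimate.

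CNS DOR is calculated in responders only (SAP 4.3.3, applied through 4.3.4), so these patients do not enter it.

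**The case against.** **The investigator-defined set is the one with scheduled CNS follow-up.** Protocol Table 7-1 (footnote v) and the notes in Protocol 7.3 tie serial brain imaging to CNS disease at baseline, with other brain scans only if clinically indicated. They do not name the reader, and no return of IRC reads to sites is described, so in practice the site's reading would probably govern. This stands, and it limits the remedy. A reader might infer that the main set should simply be redefined by the IRC read, so that patients with lesions seen only by the IRC are brought in. The documents do not support that. Those patients may have no scheduled follow-up brain scans, and would enter the denominator with little chance of a confirmed response, which is the same fault in another form.

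**IRC baseline brain reads are not guaranteed outside the set.** Table 7-1 footnote v, Protocol 7.8.2 and Appendix G make central collection certain but central reading optional or partial. This also stands: a fully IRC-defined set cannot be assumed to need only a change of wording.

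**The IRC charter may already deal with such patients.** It may, and we cannot see it. But the SAP calls on the charter for assessment, and itself sets the analysis set and the estimator. A rule that changes the denominator belongs in the SAP.

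**The effect is conservative and the endpoint is secondary.** Both are true, and Protocol 8.3 attaches no hypothesis or sample size to CNS ORR. SAP 4.3.1 also tabulates best-response categories, including inevaluable, so part of the problem may show there. That row would still mix patients with no IRC lesion with those inevaluable for other reasons.

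**Conclusion.** The mismatch between the reader of the set and the reader of the endpoint is explicit. That patients without an IRC baseline lesion are counted as non-responders is a sound inference from the SAP as written. It is not a stated rule, and it is subject to whatever the charter says.

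The size is CNS ORR × (1 − d). The number of affected patients is unknown; every percentage above rests on assumed values of d, R and set size, and nothing in the documents shows that d is as large as 10%.

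Three stronger readings go too far. A reader might infer that the plan overstates CNS activity; the dilution calculated here runs downward. A reader might infer that responses in patients with lesions seen only by the IRC are being lost; without scheduled brain scans that is largely hypothetical, and the formula does not cover it. A reader might infer that the investigator-defined set is wrong in itself; the protocol names no reader, so it is a permissible choice. What is missing is the companion estimate that separates reader disagreement from lack of response. Adding it is a cheap improvement.

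**What to change.** 1. In SAP Table JZJA.2.2, add an IRC-confirmed CNS set: patients already in the investigator-identified CNS Response Analysis Set in whom the IRC also identifies a CNS lesion at baseline.
2. In SAP 4.3.4, report IRC CNS ORR with its exact 95% CI in that set, alongside the investigator-defined set.
3. State how a patient with no IRC baseline CNS lesion is counted in the investigator-defined set, and tabulate the number of such patients.
4. Do not add patients with lesions seen only by the IRC to either denominator by default. If IRC reads exist for them, list them separately.

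**Cost.** An amendment to SAP wording and one more table. The baseline IRC reads in the investigator-identified patients are needed for the endpoint anyway, so no new imaging is required. The statistical price is a smaller denominator and a wider interval in the confirmed set.
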